12.2. Adverse Event Reporting Period

The AE reporting period for this study is continuous and begins at the time of randomization to study treatment and ends on Study Day 29.

In addition, any known untoward event that occurs subsequent to the AE reporting period that the Investigator assesses as related to the investigational medication should also be reported as an AE.

All AEs (both serious and nonserious) must be followed until resolution or until a stable clinical endpoint is reached. All measures required for AE management and the ultimate outcome of the AE must be recorded in the source documentation and in the eCRF.

12.3. Treatment Emergent Adverse Events

Treatment-emergent AEs are defined as those that begin or worsen after the start of study drug administration.

12.4. Recording of AEs

All AEs will be documented in the appropriate section of the eCRF.

NOTE: Symptoms and events associated with SARS-CoV-2 infection will be scored as per the SARS-CoV-2 infection symptom score (Table 2) and the Ordinal Scale for Clinical Improvement (Table 4). These findings should not be reported as Adverse Events.

In the event that the electronic data capture (EDC) system cannot be accessed and a SAE or serious suspected adverse reaction has occurred, a paper SAE report form will be available to be completed and faxed or emailed to the Sponsor or their designee.

The following will be recorded for each AE in the eCRF:

- A description of the AE in medical terms. Whenever possible, a diagnosis should be given when signs and symptoms are due to common etiology (e.g., cough, runny nose, sneezing, sore throat, and head congestion should be reported as "upper respiratory infection")
- Start date
- Stop date
- The severity (i.e., grade) as assessed by the Investigator according to the definitions in the Toxicity Grading Scale for Healthy Adult and Adolescent Volunteers Enrolled in Preventive Vaccine Clinical Trials. If the AE is not specifically listed in the reference above, the following grades should be used:
 - Grade 1 Mild; asymptomatic or mild symptoms; clinical or diagnostic observations only; intervention not indicated
 - Grade 2 Moderate; minimal, local or noninvasive intervention indicated; limiting ageappropriate instrumental ADL (Activities of Daily Living)
 - Grade 3 Severe or medically significant but not immediately life threatening; hospitalizaton or prolongation of hospitalization indicated; disabling; limiting self-care ADL
 - o Grade 4 Life-threatening consequences; urgent intervention indicated
 - Grade 5 Death related to AE
- The causal relationship to study drug as assessed by the Investigator; the decisive factor in the documentation is the temporal relation between the AE and the study drug.
- Action(s) taken (e.g., study drug administration interrupted, study drug not administered, none, unknown).
- The outcome (e.g., recovered/resolved, not recovered/not resolved, recovering/resolving, recovered/resolved with sequelae, fatal, unknown).

• Whether it caused the subject to discontinue the study.

If in any 1 subject the same AE occurs on several occasions (unless the AE is continuous and of stable grade), the AE in question will be documented and assessed at each occurrence.

Should a pregnancy of a female participant or a partner of a male participant occur, it must be reported and recorded in the eCRF. Pregnancy in itself is not regarded as an AE unless there is suspicion that an investigational product may have interfered with the effectiveness of a contraceptive medication.

The outcome of all pregnancies (spontaneous miscarriage, elective termination, normal birth, or congenital abnormality) must be followed up and documented even if the subject was discontinued from the study.

All reports of congenital abnormalities/birth defects are SAEs. Spontaneous miscarriages should also be reported and handled as SAEs. Elective abortions without complications should not be handled as AEs.

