12.1. Definitions

Adverse Event (AE)

An AE is any untoward medical occurrence associated with the use of a drug in humans, whether or not considered drug related.

An AE can therefore be any unfavorable and unintended sign (including an abnormal laboratory finding, for example), symptom, or disease temporally associated with the use of a medicinal (investigational) product, whether or not related to the medicinal (investigational) product.

An abnormal laboratory value will be considered an AE if it qualifies as such based on the Toxicity Grading Scale for Healthy Adult and Adolescent Volunteers Enrolled in Preventive Vaccine Clinical Trials.

Throughout the course of the study, every effort should be made to remain alert to possible AEs. Subjects should be encouraged to report AEs spontaneously or in response to general, nondirected questioning.

With the occurrence of an AE, the primary concern is the safety of the subject. Appropriate management of the AE should always be the first priority.

Suspected Adverse Reaction

Defined as any adverse event for which there is a reasonable possibility that the drug caused the adverse event. For the purposes of IND safety reporting "reasonable possibility" means there is evidence to suggest a causal relationship between the drug and the adverse event. Suspected adverse reaction implies a lesser degree of certainty about causality than adverse reaction, which means any adverse event caused by the drug.

Life-Threating Adverse Event or Life-Threatening Suspected Adverse Reaction

An adverse event or suspected adverse reaction is considered "life-threatening" if, in the view of either the investigator or sponsor, its occurrence places the patient or subject at immediate risk of death. It does not include an adverse event or suspected adverse reaction that, had it occurred in a more severe form might have caused death.

Serious Adverse Event (SAE) or Serious Suspected Adverse Reaction

The terms "serious" and "severe" are not synonymous. Adverse events classified as "serious" have defined regulatory requirements. Those classified as "severe" do not have defined regulatory requirements unless they are also classified as "serious".

The term "severe" is often used to describe the intensity of a specific event (as in mild, moderate, or severe myocardial infarction); the event itself, however, may be of relatively minor medical significance (such as severe headache).

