12.5. Assessing Relationships of AE to Study Drug

The Investigator must record his/her opinion concerning the relationship of the AE to study therapy on the AE eCRF. Table 3 provides guidance for assigning relationship to the study drug.

able 3:	Relationship of	f Adverse l	Event to the	Administration	of the	Study	Drug
able 3:	Relationship of	f Adverse l	Event to the	Administration	of the	Study	r

Unrelated	There is not a temporal relationship to study drug or there is a reasonable causal relationship between another drug, concurrent disease, or circumstance and the AE. The AE is clearly not related to study drug .		
Unlikely	There is a temporal relationship to study drug, but there is not a reasonable causal relationship between the study drug and the AE. The AE is doubtfully related to study drug .		
Possibly	There is a reasonable causal relationship between the study drug and the AE. The AE may be related to study drug.		
Probably	There is a reasonable causal relationship between the study drug and the AE The AE is likely related to the study drug .		
Definitely	There is a causal relationship between the study drug and the AE. The AE is clearly related to the study drug .		

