7.2.5 Adverse Event Summaries

All AEs (serious and non-serious) occurring after randomization and before the end of study, regardless of relationship to study drug, will be included and classified by SOC and PT using MedDRA.

For TEAEs, the following will be summarized and presented:

- i. An overall summary of TEAEs, which includes:
 - a. the number and percentage of subjects experiencing a TEAE
 - b. the number and percentage of subjects experiencing a TEAE by strongest relationship to study drug
 - c. the number and percentage of subjects experiencing a TEAE by greatest severity
 - d. the number and percentage of subjects experiencing a treatment-emergent SAE
 - e. the number and percentage of subjects experiencing a TEAE leading to death
 - f. the number and percentage of subjects experiencing a TEAE leading to study withdrawal
- ii. the number and percentage of subjects experiencing a TEAE by SOC and PT.
- iii. the number and percentage of subjects experiencing a potentially related TEAE by SOC and PT, where a potentially related TEAE is defined as any TEAE with a causal relationship to study drug assessed as 'Possibly Related', 'Probably Related', or 'Definitely Related'.
- iv. the number and percentage of subjects experiencing a TEAE by SOC, PT and the strongest relationship to study drug
- v. the number and percentage of subjects experiencing a TEAE by SOC, PT and the greatest severity
- vi. the number and percentage of subjects experiencing a treatment-emergent SAE by SOC and PT
- vii. the number and percentage of patients experiencing a TEAE leading to death by SOC and PT
- viii. the number and percentage of subjects experiencing a TEAE leading to study withdrawal by SOC and PT

In the overall summary of TEAEs table (i), besides tabulating the number and percentage of subjects, the total number of TEAE episodes will also be provided. If a subject has repeated episodes of a particular TEAE, all episodes will be counted in the summary table.

In the remaining summary tables, the incidence of TEAEs will be calculated by dividing the number of subjects who have experienced the event by the total number of subjects. Thus, the incidence of TEAEs is shown in terms of the total number of subjects and not in terms of the total number of episodes. If a subject has repeated episodes of a particular TEAE, only the most severe episode, or the episode with the strongest causal relationship to study drug, will be counted in the summary tables.

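### Protocol 12.4 makes timing the decisive factor in adverse-event causality, which conflicts with Table 3 in 12.5 and could distort the related-event counts

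*Protocol*

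**What the plan says.** **Protocol 12.4 (Recording of AEs)** lists what goes into the eCRF for each event. For the causal relationship it names the investigator's assessment and then adds that "the decisive factor in the documentation is the temporal relation between the AE and the study drug". It gives no window, does not mention alternative causes, and does not refer to Table 3.

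**Protocol 12.5 and Table 3** cover the same field. "The Investigator must record his/her opinion concerning the relationship of the AE to study therapy on the AE eCRF", and "Table 3 provides guidance for assigning relationship to the study drug". Two of the five categories address timing directly:

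- Unlikely: "There is a temporal relationship to study drug, but there is not a reasonable causal relationship between the study drug and the AE".
- Unrelated applies where the timing does not fit, or where some other drug, illness or circumstance reasonably accounts for the event.

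Possibly, Probably and Definitely rest on a causal relationship and do not mention timing. Possibly and Probably share one criterion sentence; only the closing gloss differs (may be related, against likely related).

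**Protocol 12.3** defines treatment emergence: "Treatment-emergent AEs are defined as those that begin or worsen after the start of study drug administration". **Protocol 12.2** closes the reporting period on Day 29 and asks for later events only where the investigator judges them related.

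**SAP 7.2.3** sends the reader to Protocol 12.5 for the relationship categories and does not mention 12.4. **SAP 7.2.5**, item iii, tabulates potentially related events, meaning "any TEAE with a causal relationship to study drug assessed as" possibly, probably or definitely related. Items i.b and iv report events by strongest relationship. Items i.a and ii count all treatment-emergent events whatever their assessed cause.

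**The concern.** An investigator completing the causality field meets two instructions that need not give the same answer. Take a headache on the day after a dose with an evident other cause. Under Table 3 it is Unrelated. If timing decides, as 12.4 says, the entry is pushed towards related.

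The field feeds three planned displays (SAP 7.2.5 items i.b, iii and iv) and the decision on reporting events after Day 29. Tolerability is a stated secondary objective. The protocol allows up to 20 centres, and nothing in it says which instruction takes precedence, so sites could resolve the conflict differently. Related counts would then reflect site practice as well as the drug.

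**Working it through.** The documents give no figure for causality, so there is none to reproduce. The check is a comparison of texts, followed by two illustrations on stated assumptions.

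**1. The two instructions side by side**

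| Event | 12.4 taken literally | Table 3 |
|---|---|---|
| Close to a dose, no reasonable causal link to study drug | points to related | Unlikely |
| Close to a dose, another cause reasonably explains it | points to related | Unrelated |
| Close to a dose, reasonable causal link to study drug | points to related | Possibly or higher |
| No temporal relationship | points to not related | Unrelated |

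They part in the first two rows, which are the background events. Under Table 3 those events stay out of SAP item iii; under a literal 12.4 they enter it.

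**2. How many unrelated events timing alone would capture**

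Inputs: doses on Days 1, 3, 6 and 10 (Protocol 7.1) and reporting to Day 29 (Protocol 12.2). Assumptions, not in the documents: unrelated events start uniformly over Days 1 to 29, and a temporal relation means onset from 0 to w days after some dose.

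Share(w) = number of days d from 1 to 29 with 0 ≤ d − dose ≤ w for at least one dose, divided by 29. The largest gap between doses is 4 days, so for w of 3 or more every day up to Day 10 + w qualifies and the share is (10 + w)/29.

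| w (days) | Qualifying days | Share |
|---|---|---|
| 1 | 8 | 8/29 = 28% |
| 2 | 11 | 11/29 = 38% |
| 3 | 13 | 13/29 = 45% |
| 5 | 15 | 15/29 = 52% |
| 7 | 17 | 17/29 = 59% |
| 14 | 24 | 24/29 = 83% |

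The shares apply equally to both arms. Since 12.4 gives no window, a site's answer could lie anywhere in this range.

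**3. Outer limit on the related-event table**

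Suppose every treatment-emergent event were labelled related. Let b be the background risk of an event and a the risk added by the drug (both assumed). The active-arm risk is 1 − (1 − b)(1 − a), and the difference between arms is a(1 − b).

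- With b = 20% and a = 10%: active 1 − 0.80 × 0.90 = 28%, placebo 20%, difference 8 points. Perfect attribution would show 10% against 0%.
- With b from 10% to 40% and a from 5% to 15%: the difference runs from 0.05 × 0.60 = 3.0 points to 0.15 × 0.90 = 13.5 points.

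Both arms are inflated, but the difference between them remains. At this limit item iii simply becomes the all-event table.

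**4. Events after Day 29**

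By schedule, an event on Day 30 falls 30 − 10 = 20 days after the last dose. Whether that counts as a temporal relation depends wholly on the unstated window. If timing decides, such an event could be reported or left out with no change in the evidence on its cause.

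**The case against.** The strongest reply is that 12.4 lists data fields and is not a classification rule. It defines no categories, it says in the same item that the investigator makes the assessment, and Table 3 is the named guidance. The SAP relies on 12.5 alone. All of this stands. It means that misclassification is a risk at sites that follow 12.4 literally, not something the plan guarantees. It does not remove the conflict: calling timing decisive cannot be squared with a table in which an event that fits in time may be Unlikely or Unrelated.

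Four stronger readings are tempting, and the documents do not support them.

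- *Timing is met by every treatment-emergent event, so the criterion is empty.* A temporal relation can mean closeness to a dose, not merely onset after the first one. Table 3 needs that sense, since its no-temporal-relationship limb could otherwise never apply to a treatment-emergent event. By schedule the interval from the latest dose runs from minutes to 29 − 10 = 19 days. With a 3-day window, 16 of 29 days (55%) would not qualify.
- *The trial cannot separate drug effects from background events.* The all-event displays (items i.a and ii) compare randomised arms under blinding and do not use the causality field. Even at the outer limit above, the arm difference survives.
- *The SAP tables contradict Table 3.* They use Table 3's own categories. The inconsistency lies in one clause of Protocol 12.4.
- *Protocol 12.1 adds a third conflicting rule.* Its wording, that reasonable possibility "means there is evidence to suggest a causal relationship between the drug and the adverse event", is introduced for IND safety reporting. It is not a criterion for the eCRF relationship grade.

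It is also fair to say that relatedness is not among the safety and tolerability endpoints in SAP 2.2.3, and that SAP Section 7 plans no formal safety testing. Making the all-event table the declared lead display would therefore be a preference, not a correction.

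**Conclusion.** The clause in Protocol 12.4 is inconsistent with Table 3 and should be corrected. Followed literally, it could move background events near a dose into the related categories, inflating SAP 7.2.5 items i.b, iii and iv or making them inconsistent across sites, and it would affect reporting after Day 29. Under the uniform-onset assumption, timing alone would capture 45% to 83% of unrelated events for windows of 3 to 14 days. How many events would actually be misclassified cannot be known from the documents, because it depends on how sites read the clause.

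The loss is in the specificity of the relatedness displays. The all-event comparison by arm, the primary endpoint and the sample size are not affected.

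A secondary point holds as well. Because Possibly and Probably share a criterion sentence, the split between them in items i.b and iv rests on the gloss alone. Item iii pools the two and is unchanged.

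**What to change.** In Protocol 12.4, delete the clause on the decisive factor and replace it with: 'assessed by the Investigator according to Table 3 (Section 12.5)'. Carry the same reference into any eCRF completion guidance. The SAP needs no change here, since 7.2.3 already refers to 12.5.

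As a secondary improvement, give Possibly and Probably distinct criteria in Table 3, for example another cause about equally likely against other causes less likely.

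The cost is a small protocol amendment with no new data collection. The one downside is a single re-check, under blinding, of relatedness already recorded, so that all events are classified on the same basis before the related-event tables are produced.

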12.5. Assessing Relationships of AE to Study Drug

The Investigator must record his/her opinion concerning the relationship of the AE to study therapy on the AE eCRF. Table 3 provides guidance for assigning relationship to the study drug.

able 3:	Relationship of	f Adverse l	Event to the	Administration	of the	Study	Drug
able 3:	Relationship of	f Adverse l	Event to the	Administration	of the	Study	r

Unrelated	There is not a temporal relationship to study drug or there is a reasonable causal relationship between another drug, concurrent disease, or circumstance and the AE. The AE is clearly not related to study drug .		
Unlikely	There is a temporal relationship to study drug, but there is not a reasonable causal relationship between the study drug and the AE. The AE is doubtfully related to study drug .		
Possibly	There is a reasonable causal relationship between the study drug and the AE. The AE may be related to study drug.		
Probably	There is a reasonable causal relationship between the study drug and the AE The AE is likely related to the study drug .		
Definitely	There is a causal relationship between the study drug and the AE. The AE is clearly related to the study drug .		

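### An adverse event with two reasonable causes meets both the 'Unrelated' and the 'Possibly'/'Probably' rows of Protocol Table 3, so the relationship-based safety tables can lose it or code it inconsistently

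*Protocol*

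**What the plan says.** Protocol Section 12.5 asks the investigator for an opinion on causality and says that "Table 3 provides guidance for assigning relationship to the study drug".

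- The *Unrelated* row has two conditions joined by 'or'. The first is that timing does not link the event to the study drug. The second is that "there is a reasonable causal relationship between another drug, concurrent disease, or circumstance and the AE". The row closes with "The AE is clearly not related to study drug".
- *Possibly* and *Probably* open with the same sentence: "There is a reasonable causal relationship between the study drug and the AE". Neither mentions competing causes. Only their closing sentences differ: the event may be related, or is likely related.
- The table gives no rule for an event that fits more than one row.

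Two other protocol sections bear on the same judgement. Section 12.4, on recording causality, says that "the decisive factor in the documentation is the temporal relation between the AE and the study drug". Section 12.1 describes a suspected adverse reaction: "Defined as any adverse event for which there is a reasonable possibility that the drug caused the adverse event". It makes no exception for an event that also has another plausible cause.

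SAP Section 7.2.3 takes over the five protocol levels and refers back to Section 12.5 without adding definitions. In SAP Section 7.2.5 item iii, "a potentially related TEAE is defined as any TEAE with a causal relationship to study drug assessed as" one of the top three levels. Items i.b and iv report events by strongest relationship.

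**The concern.** A causality scale should place each event in one row. Here an event for which both the study drug and something else are reasonable causes fits at least two rows, which lie on opposite sides of the SAP's cut-off for potentially related events. With up to 20 centres (Protocol 7.5), the same clinical picture can be rated differently by investigators who all follow the table.

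The setting makes such events plausible. Recent exposure to SARS-CoV-2 is an entry condition (7.2.1), so a competing circumstance is to hand for some respiratory events. The drug itself produced a dose-dependent fall in FEV1 in the first phase 1 study (5.4), and the post-dose guidance names cough and shortness of breath as symptoms to watch for (7.10.2, 7.11.2). Tolerability is a secondary objective (6.2). What is at stake is whether the count of events judged potentially related means what its label says.

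**Working it through.** No figure in the plan bears on this point, so the check is logical. Take three yes/no facts about an event: T, there is a temporal relation to dosing; D, the study drug is a reasonable cause; A, something else is a reasonable cause. From the criterion sentences of Table 3:

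- *Unrelated* is met if T is no, or A is yes.
- *Unlikely* is met if T is yes and D is no.
- *Possibly* and *Probably* are each met if D is yes.
- *Definitely* asserts an outright causal relationship and is left aside.

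| T | D | A | Rows met | Same side of the item iii cut-off? |
|---|---|---|---|---|
| yes | yes | yes | Unrelated, Possibly, Probably | No |
| yes | yes | no | Possibly, Probably | Yes (counted) |
| yes | no | yes | Unrelated, Unlikely | Yes (not counted) |
| yes | no | no | Unlikely | Yes (not counted) |
| no | yes | either | Unrelated, Possibly, Probably | No |
| no | no | either | Unrelated | Yes (not counted) |

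The first line is the problem. The fifth arises only because the *Possibly* and *Probably* criteria state no temporal condition, and is largely theoretical.

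For the first line, compare the other text. The closing sentence of the *Unrelated* row cannot be true of an event for which the drug is a reasonable cause, so the row disagrees with its own second condition. Section 12.4 makes timing decisive, yet the second condition lets an event that follows dosing be *Unrelated*. Section 12.1 would treat the event as a suspected adverse reaction, yet Table 3 permits *Unrelated*.

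Consequence in SAP 7.2.5: rated *Possibly*, the event enters item iii; rated *Unrelated*, it does not. Items i.b and iv show it at a different level. Items i.a, i.c to i.f, ii and v to viii do not use the rating and are unchanged.

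Size: let f be the share of otherwise potentially related events that also have a reasonable competing cause, and g the share of those rated *Unrelated*. The fraction lost from item iii is f × g. The documents give neither quantity, so the result can lie anywhere from 0 to 1. Assuming f between 1/3 and 2/3 with g = 1 gives a loss of 1/3 to 2/3, which merely returns the assumption.

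**The case against.** The strongest reply is that the table is guidance, and that its closing sentences settle the matter: an investigator who thinks the drug a reasonable cause cannot endorse a statement that the event is clearly unrelated, and would choose *Possibly*. That is a fair account of what a careful rater would do, and it shows that the table does not instruct anyone to choose *Unrelated*. But the criterion as written still permits it, and nothing says that the closing sentence overrides the criterion.

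Several stronger readings might be inferred, and the documents do not support them:

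- *That the tolerability result is biased or an arm difference hidden.* The safety endpoints in SAP 2.2.3 are all TEAEs, all treatment-emergent SAEs, FEV1 reduction and vital signs, none filtered by relationship. FEV1 falls are tabulated by size on each dosing day (SAP 7.3). The DSMB reviews any AE imbalance between arms (Protocol 14.4). Investigators are blinded (SAP 3.2.2), so the ambiguity applies to both arms.
- *That serious events could go unreported.* Section 12.6 requires every SAE to be reported within 24 hours, whatever its relationship, and Section 12.1 does not make Table 3 the test for a suspected adverse reaction.
- *That most respiratory events have SARS-CoV-2 as a competing cause in Table 3.* Symptoms associated with the infection are scored separately and are not reported as AEs (Sections 12 and 12.4), so they receive no rating. Subjects enter symptom-free, and the protocol calls the post-dose lung-function fall usually asymptomatic.
- *That Possibly and Probably cannot be told apart.* Their closing sentences separate them, and item iii pools them.

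These points narrow the consequence. They do not remove the overlap.

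**Conclusion.** The defect holds as a matter of wording: the alternative-cause condition is sufficient for *Unrelated* without excluding the study drug, so a dual-cause event fits rows on both sides of the SAP's cut-off with no precedence rule. The row contradicts its own closing sentence and is at odds with Sections 12.1 and 12.4.

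The effect is limited to possible loss from SAP 7.2.5 item iii and inconsistent coding in items i.b and iv. The size cannot be computed from the documents, and no percentage should be attached to it. The conclusion rests on reading the criterion sentences as operative. If every investigator let the closing sentence govern, nothing would be lost. It is worth correcting because the remedy is small and a later SAP change cannot recover judgements already made; it is not a threat to the main safety comparison.

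**What to change.** Reword Table 3 and repeat the change in a site memo:

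- *Unrelated*: no temporal relationship, or another cause explains the AE and there is no reasonable possibility that the study drug contributed.
- Add beneath the table: a competing cause alone does not make an AE Unrelated.
- Give *Possibly* and *Probably* different criteria that match their existing closing sentences. For example, *Possibly* where another cause is equally or more plausible than the drug, and *Probably* where other causes are less plausible.
- Align the table with Sections 12.1 and 12.4, so that *Possibly* or above, as counted in SAP 7.2.5 item iii, corresponds to a reasonable possibility of drug causation. SAP item iii lists rating levels and does not itself refer to Section 12.1, so the correspondence has to be built into the table.

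The revised *Unrelated* wording still shares one case with *Unlikely*: timing fits, the drug is not a reasonable cause, and something else is. Both levels fall below the cut-off, so item iii is unaffected. Limiting *Unlikely* to events that no other cause explains would separate them for items i.b and iv.

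The cost is one table and one memo, made before ratings are entered, and a somewhat higher potentially related count.
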